
Primary aim: To compare mean weight loss between the *GR* and *IH* arms across 6 mos. We expect significantly greater weight loss in the *GR* compared to the *IH* arm.

Secondary aims. *To compare the GR and IH arms on the following:* 1) Mean weight loss (0-18 mos.); 2) The proportion of participants who achieve clinically significant weight loss ($\geq 5\%$ from baseline) at 18 mos.; 3) Changes in cardiovascular disease risk factors (blood pressure, total, HDL and LDL cholesterol, triglycerides, HbA1c for diabetics, waist circumference) from 0-6 and 0-18 mos.; 4) Changes in quality of life from 0-6 and 0-18 mos. We expect more favorable changes in all secondary outcomes in the GR compared with the IH arms. 5) Cost and contingent valuation analysis to compare costs between the GR and IH arms. Based on our experience with remote delivery for weight management using both group phone (DK76063) and virtual reality formats (DK94833), we expect GR to be less expensive than the IH arm.

Exploratory aims. *Initial weight loss is highly predictive of longer-term weight loss; therefore, we will examine the influence of the following variables on weight loss at 6 and 18 mos.:* behavioral session attendance, compliance with the recommendations for diet (energy intake, number of meals /shakes, servings of fruits/vegetables), PA (min of moderate-vigorous PA, min sedentary time), and self-monitoring of diet and PA, self-efficacy for dietary change and PA, dietary self-regulation, social support for diet/PA, barriers to PA, sleep, and medications.

BACKGROUND/SIGNIFICANCE

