Cost analysis ([name]). A cost analysis may be considered premature. However, this may be the only opportunity we will have to complete such analyses, which can be done at minimal expense, in a large sample of adults with MRDs. Based on a previous weight loss trial (71) we expect higher costs associated with health educator travel required in the *IH* arm. Mean weight loss at 6 mos. will serve as our measure of effectiveness. We expect greater weight loss and lower costs in the *GR* compared with the *IH* arms (150). We will then calculate the cost per additional kg of weight loss. Contingent valuation analysis, in which participants express preferences for programs, will be used to examine the perceived worth of the *GR* and *IH* formats at 6 and 18 mos.(151). Conditional logistic regressions, with adjustments for clustering by health educator, will be used to analyze how differences in client attributes, anticipated costs, and anticipated gains affect preferences for the 2 intervention arms. The cost perspective for all

analyses will be societal. We will collect data on both program and participant costs prospectively. The gold standard for measuring cost is a time study based on a validated flowchart (152, 153). We will validate flowcharts for both study arms and use time studies to estimate health educator time, and program records to measure cost of supplies. Participant time, valued at the local median hourly wage, is also a component of intervention costs (154) as time devoted to an intervention cannot be used for work or leisure. These costs may be half of the total costs (155, 156) and will be gathered via survey (157).

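### The only measure joining cost and effect is a cost per extra kilogram lost, which cannot be interpreted if GR is both cheaper and better, as the plan expects

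*Combined protocol and SAP*

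**What the plan says.** Secondary aim 5 (Aims and Hypotheses) is described as "Cost and contingent valuation analysis to compare costs between the GR and IH arms", with the prediction that "we expect GR to be less expensive than the IH arm".

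The Cost analysis section, under Outcome Measures, fixes the effect measure: "Mean weight loss at 6 mos. will serve as our measure of effectiveness". It gives the expected direction of both components, "We expect greater weight loss and lower costs in the" GR arm, and continues: "We will then calculate the cost per additional kg of weight loss". It also plans a second strand: "Contingent valuation analysis, in which participants express preferences for programs, will be used to examine the perceived worth of the" two delivery formats at 6 and 18 months, with a regression model for participants' preferences. On perspective, it says that "analyses will be societal", and of participant time that "These costs may be half of the total costs".

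The section describes how costs are measured. It does not say how the cost difference will be estimated, what interval will accompany it or the ratio, what will be reported if the ratio is negative, or what a kilogram of weight loss is taken to be worth. Analysis plans covers the primary aim, secondary aims 1 to 4 and the exploratory aims. It does not cover aim 5.

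**The concern.** An incremental cost-effectiveness ratio answers one question: how much extra is paid for each extra unit of benefit. It has a plain reading when one arm costs more and does more. When one arm costs less and does more, nothing is being traded. The ratio turns negative, and its size no longer measures how good the result is.

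The protocol predicts this second case and names the ratio as the quantity to compute, with no alternative. If the prediction comes true and the text is followed, the trial's one cost-effectiveness figure would be a negative dollar amount per kilogram that a reader cannot interpret without its two components.

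**Working it through.** **Inputs from the documents** (Power/sample size): weight-loss difference 3 kg, SD 6 kg, 64 per group, type 1 error 0.05, power 80%. Sidedness is not stated; two-sided is used because it reproduces the plan's figure.

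**Inputs assumed**, because the documents contain no cost figures: the cost difference, a cost SD of $500 per participant, and a value of $100 per kg. They show how the measure behaves and do not estimate this trial's costs.

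**1. The plan's own figure.** n per group = 2 × (1.96 + 0.842)² × 6² / 3² = 2 × 7.85 × 4 = 62.8, so 63 by the normal approximation. The t-test version gives 63.8, so 64. The stated size reproduces.

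**2. Behaviour of the ratio.** Let ΔC and ΔE be cost and weight loss, GR minus IH. The ratio is R = ΔC/ΔE. Incremental net benefit is NB = λ × ΔE − ΔC, with λ = $100 per kg.

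| GR compared with IH | ΔC ($) | ΔE (kg) | R ($/kg) | NB ($) |
|---|---|---|---|---|
| Cheaper, better | −300 | +3 | −100 | +600 |
| Dearer, worse | +300 | −3 | −100 | −600 |
| Cheaper, smaller gain | −300 | +1 | −300 | +400 |
| Cheaper, larger gain | −300 | +6 | −50 | +900 |
| Cheaper by less, small gain | −100 | +1 | −100 | +200 |
| Cheaper by more, large gain | −600 | +6 | −100 | +1,200 |
| Dearer, better | +300 | +3 | +100 | 0 |

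The first two rows are opposite findings with the same ratio. Rows 1, 3 and 4 hold the saving at $300: as the gain rises from 1 to 3 to 6 kg, R moves from −300 to −100 to −50. Rows 5 and 6 are very different results that share −$100/kg. Net benefit orders all of them sensibly. In the last row the ratio has its ordinary reading of $100 paid per extra kilogram.

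**3. How likely the problem case is under the plan's expectations.** SE(ΔE) = 6 × √(2/64) = 1.06 kg. With the assumed cost SD, SE(ΔC) = 500 × √(2/64) = $88. Drawing 400,000 independent normal pairs at a true ΔE of 3 kg:

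- ΔC = −$600: 99.8% of results have GR cheaper and better
- ΔC = −$300: 99.7%
- ΔC = −$100: 87%
- ΔC = $0: 50%
- ΔC = +$300: 99.7% have GR dearer and better, where the ratio works

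The draws ignore any correlation between cost and effect and any sharing of costs within GR groups.

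**4. Is the denominator near zero?** At 3 kg, 3/1.06 = 2.8 standard errors. The expected 95% interval is 3 ± 2.08, or 0.9 to 5.1 kg, and the chance of an estimate at or below zero is about 0.2%. At a true difference of 1.5 kg that chance is about 8%, and with ΔC = −$300 the simulated ratio runs from −1,867 to +1,440 $/kg (2.5th to 97.5th percentiles).

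**The case against.** The best defence is that the ratio is one sentence in a wider plan. A reader might infer that the whole economic analysis is this ratio, or that aim 5 cannot be tested. The documents support neither. Aim 5 predicts that GR costs less; the between-arm cost difference tests that and keeps its meaning whichever arm loses more weight. The contingent valuation does not depend on the ratio. Incremental 6-month weight loss is reported anyway as the primary result, so a careful reader could recognise dominance from the two components. With only two arms, there is also no list of options for the ratio to misorder. All of this stands, and it limits the harm.

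Lower GR cost is also a prediction only. The perspective is societal, participant time may be a large share of cost, and Study Type and Design moves Cohort 1 IH meetings to the telephone, which removes the travel for those meetings. If GR proves better but dearer, the ratio is the right summary. That is a reason to keep it for that case. It is also a reason to specify reporting that works whichever way the costs fall.

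A reader might further infer that the ratio is unstable in the planned scenario because its denominator could approach zero. Step 4 shows otherwise: instability matters only if the true difference is well below 3 kg.

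Finally, the sentence might mean an average cost per kilogram within each arm, which would stay positive if both arms lose weight. The word for extra kilograms points to the incremental reading. If averages were meant, the text should say so.

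What the defence does not supply is any rule for dominance, any interval for the cost difference, or any joint summary of cost and effect.

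**Conclusion.** The point holds in limited form. In the result the plan itself predicts, its only joint measure of cost and effect is negative, takes the same value for GR dominating and GR being dominated, and moves toward zero as the weight benefit grows. This follows from the algebra and does not depend on the dollar values chosen. Those values affect only how often the case arises: at the planned 3 kg difference, from about half of results with no true cost difference to nearly all with a $300 saving, given the assumed cost SD of $500.

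The consequence is confined to one reported figure within a secondary aim. The cost comparison, the contingent valuation, the primary analysis and the sample size are unaffected. It is a reporting improvement of low severity.

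**What to change.** Amend the Cost analysis section so that it:

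1. Reports incremental cost and incremental 6-month weight loss separately, each with a bootstrap interval, and shows their joint distribution on the cost-effectiveness plane.
2. States that dominance will be declared if one arm is cheaper and better.
3. Gives incremental net benefit over a stated range of values per kilogram. The documents give no such value, so the range must be labelled an assumption.
4. Reports the ratio only when one arm is both dearer and better.

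The resampling should respect the GR session groups. Their delivery costs are shared among the 10 to 15 people in a session, so resampling individuals alone could misstate the uncertainty. Sixty-four participants in groups of that size make only 5 or 6 groups (64/5 = 12.8; 64/6 = 10.7), so intervals based on resampling groups will be rough and should be described that way.

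The cost is a paragraph of text, some extra analysis, and a decision on the range of values per kilogram. The plan already provides for collecting program costs, participant costs and weight, so no new data are needed.

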Official Title: Weight Management for Adults with Mobility Related Disabilities

NCT Number: 04046471

Approval Date: January 26, 2024

Document: Study Protocol with Statistical Analysis Plan

AIMS AND HYPOTHESES

Individuals with mobility related disabilities (MRDs) represent a sizeable and growing segment of the U.S. adult population, with high rates of obesity, and limited options for successful weight management. Obesity in adults with MRDs increases the risk of chronic disease, and may limit the ability to ambulate, either with or without assistive devices (wheelchair, cane etc.), perform transfers (wheelchair users), increase the risk for pressure sores, respiratory problems, carpal tunnel syndrome, and interfere with self-care, and reduce participation in daily activities. Adults with MRDs face numerous barriers to participation in traditional weight management programs including the lack of affordable, accessible transportation to attend on-site meetings or engage in physical activity (PA), lack of accessible recreational facilities with accessible fitness equipment, and difficulty with food shopping and meal preparation. The 2005 Surgeon General's Call to Action to Improve the Health and Wellness of Persons with Disabilities, and numerous subsequent government sponsored reports, have highlighted the need for accessible health promotion efforts to reduce health disparities between adults with and without MRDs. However, a limited number of intervention strategies, specific to weight management in adults with MRDs, have been developed and evaluated. As described in this proposal, our group has evaluated an enhanced version of the Stop Light Diet (eSLD = SLD+portion-controlled meals and low calorie shakes) for weight management in a sample of 126 adults with MRDs. The eSLD simplifies meal planning, food shopping and meal preparation. When prescribed in conjunction with a monthly behavioral intervention, delivered in an individual home visit format, the eSLD resulted in significantly greater weight loss when compared with a conventional meal plan diet at 6 mos. (eSLD = -4.1%, meal plan = -2.3%, $p=0.02$) and 12 mos. (eSLD = -6.2%, meal plan = -0.6%, $p=0.005$). Although these results are encouraging, alternative strategies to improve outcomes and to deliver weight management to larger numbers of adults with MRDs in a cost-effective manner, are warranted. Thus, the proposed two-arm randomized trial will compare weight loss (6 mos.) and maintenance (18 mos.) between an individual home visit intervention (*IH*), using an enhanced version of the protocol used in our previous trial, and an intervention delivered remotely via video conferencing to groups of overweight/obese adults with MRDs in their homes (*GR*). Both interventions will be delivered in a format that eliminates the transportation barrier, prescribed an eSLD, and will self-monitor body weight using electronic scales. The *GR arm* will include group behavioral counseling and group PA delivered remotely via video conferencing (Zoom™ software) on a tablet computer (iPad mini) to participants in their homes, and use commercially available web-based applications for self-monitoring/participant feedback for diet (Lose It! software) and PA (Fitbit activity tracker). This approach reduces barriers to both behavioral session attendance and PA, provides timely feedback relative to diet and PA, and promotes interaction and support in a group who are often socially isolated. The *IH arm*, which represents a modified version of the protocol used in our previous trial, will include behavioral counseling delivered during individual home visits, a prescription for self-directed PA, and self-monitoring of diet and PA using conventional paper and pencil self-reports. Both groups will receive identical attention with 2 interventions having the potential for clinically meaningful weight loss, i.e., $\geq 5\%$. This trial will address the following primary, secondary and exploratory aims.

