group behavioral counseling in 16 overweight/obese adults with chronic spinal cord injury (SCI, ≥ 1 yr., age ~ 44 yrs., 100% non-ambulatory) with a 12 wk. follow-up. Results indicated small, but statistically significant weight loss at both 12 (-3.8%, $p < 0.0004$) and 24 wks. (-3.0%, $p < 0.01$). Betts & Froehlich-Grobe (56) recently reported -4.8% weight loss in a 20-wk. trial in a small sample (n=10) of adults (age ~ 49 yrs.), with MRDs (80% non-ambulatory) using the Diabetes Prevention Group Lifestyle Balance program delivered by weekly group phone calls (1-12 wks.), with 3 additional calls over the following 8 wks. Radomski et al (57) reported a median weight loss of 5.7% in a small sample of adults (n=10, age ~ 53 yrs.) with SCI (100% non-ambulatory) following a 12 wk. exercise and education intervention consisting of individualized diet and exercise recommendations, weekly on-site group nutrition and exercise education, and twice weekly exercise sessions (both group and individual). Our group recently published results from a 12 mo. trial (6 mos. weight loss, 6 mos. maintenance, NIDRR 133G090230, [name], PI) in a sample of 126 low income ($\sim 83\%$ unemployed), overweight/obese (BMI ~ 44 kg/m 2), adults (age ~ 51 yrs.) with MRDs, 71% used wheelchair or an assistive device for walking (58). Participants were randomized to a behavioral weight loss intervention that included monthly home visits by a health educator and a reduced energy conventional meal plan, or an enhanced Stop Light Diet (eSLD; 1,200-1,500 kcal/d), self-monitoring (logs), and optional PA. The Stop Light Diet, developed for use in children (59), categorizes foods by energy content corresponding to a traffic light, i.e., red (eat sparingly), yellow (eat moderately), and green (eat freely). We enhanced the SLD by encouraging daily consumption of 2 portion-controlled meals (≤ 300 kcal each), 2 high volume low energy shakes (100 kcal each), and \geq five 1-cup servings of fruits/vegetables. Mean percent weight loss was significantly greater in the eSLD compared with the meal plan groups at 6 mos. (eSLD = -4.1%, meal plan = -2.3%, $p = 0.024$) and 12 mos. (eSLD = -6.2%, meal plan = -0.6%, $p = 0.005$). The percentage of randomized participants achieving $\geq 5\%$ weight loss at 6 mos. did not differ by group (eSLD = 36%, meal plan = 23%, $p = 0.15$). However, the percentage of participants losing $\geq 5\%$ of baseline weight at 12 mos. was significantly higher in the eSLD (36%) compared with the meal plan groups (13%, $p = 0.003$).

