We propose a 2-arm randomized trial (group remote (*GR*) vs. individual home visit (*IH*)) using intent-to-treat principles, to compare body weight following weight loss (6 mos.) and maintenance (18 mos.) in overweight/obese adults with MRDs. interventions will be delivered by trained health educators and will include behavioral sessions, a reduced energy diet (eSLD), increased PA, and self-monitoring of weight using electronic scales. The *GR* arm will be delivered via video conferencing (Zoom™ software) on a tablet computer (iPad mini) with self-monitoring of diet and PA using commercially available technologies. Participants in the *IH* arm will self-monitor diet and PA using paper and pencil records. Due to COVID-19, all Cohort 1 *IH* intervention meetings will be held by phone per CDC social distancing recommendations. Participants are asked to send pictures of the tracking sheets to the health educator prior to the phone meeting. The primary outcome (weight) will be assessed during home visits at baseline (mo. 0), following weight loss (6 mos.), during (12 mos.) and at the end of maintenance (18 mos.). Our group has experience with all proposed intervention components and outcome assessments from previously completed (44, 58, 71, 78, 88, 89) or on-going trials (DK83589, HD79642). The following design attributes, described in detail subsequently, ensure the scientific rigor of the proposed trial: 1) Randomized design with equal allocation to groups, with allocation assignment concealed. 2) Adequate statistical power to address the primary aim. 3) Strategies to ensure the recruitment of sufficient participants to achieve our desired sample size. 4) Retention/incentive strategies to reduce loss to follow-up. 5) Controlling for attention by maintaining equal contact in both groups. 6) Secondary/exploratory aims to maximize the use of data, e.g., analysis to examine the impact of process variables/participant characteristics on

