Behavioral session/frequency/duration (Table 1). GR arm. Behavioral sessions (10-15 individuals) will be conducted using video conferencing (Zoom™ software) 2/mo. during weight loss and the first 6 mos. of maintenance (mos. 0-12), and 1/mo. during the last 6 mos. of maintenance (mos. 13-18). *IH arm.* Behavioral sessions will be conducted with individual participants during home visits. Behavioral sessions in the IH arm will follow the same frequency as the GR arm and will occur 2/mo. during weight loss and the first 6 mos. of maintenance (mos. 0-12), and 1/mo. during the last 6 mos. of maintenance (mos. 13-18). Meeting duration will be 45-60 min. for both groups across the intervention. Due to COVID-19, all Cohort 1 IH intervention meetings will be held by phone per CDC social distancing recommendations. Participants are asked to send pictures of the tracking sheets to the health educator prior to the phone meeting

Behavioral session content-weight loss. Behavioral sessions will be identical between groups and will include a review of participants self-monitored data for diet, PA, and weight recorded since the previous session, a question to generate discussion regarding diet and PA, a lesson on a weight management topic, and an experiential learning assignment requiring problem solving or the practice of behavioral strategies, to be completed prior to the next session. Lessons will also include topics such as cost and time efficient strategies for food shopping and

preparation, specific strategies for increasing daily PA and decreasing sedentary time, and maintaining adequate hydration, eating away from home etc., with examples and discussion questions specific to individuals with MRDs.

Behavioral session content-weight maintenance. Behavioral sessions during maintenance will focus on planning and following a meal plan diet, with or without incorporation of PCMs, and cardinal behaviors for successful weight maintenance, such as self-monitoring, regular PA, eating on weekends/vacations, and controlling energy intake on special occasions and holidays, etc.

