Energy Expenditure of Remote Exercise Sessions (optional). Energy expenditure of the remote sessions will be assessed in a volunteer sample using a previously validated portable, open-circuit indirect calorimeter (Cosmed, Italy) which measures breath-by-breath ventilation, expired oxygen, and carbon dioxide. The flow turbine will be calibrated using a 3.0-L syringe. The lightweight (~1.5 kg) portable system will be attached by a harness around the waist and shoulders of the participant before each assessment. During exercise sessions, participants will breathe into a facemask that directs air into the unit housing the O₂ and CO₂ analyzers. Data will be retrieved for analysis via a serial port interface and software provided with the calorimeter, and aggregated over 20-second epochs for the calculation of 1-min averages. MET levels will be age corrected using the Schofield equation (88) as recommended by McMurray et al (89). Participants will be asked to wear wrist ActiGraphs during the assessment for comparison of physical activity levels between devices.

SAMPLE SIZE, STATISTICAL METHODS, AND POWER CALCULATION

Power/sample size. The mean 6 mo. weight loss in our completed trial in adults with MRDs, using a protocol similar to the *IH* arm in the proposed trial, i.e., eSLD and behavioral counseling delivered by monthly home visits, was 5.5 kg (58). This does not reach the 8.5 kg (~5%) average 6 mo. weight loss defined as clinically meaningful by current weight management guidelines (53). We expect 6 mo. weight loss in the *GR* arm, which includes weekly group counseling and group exercise, will reach or exceed 8.5 kg. To detect a clinically meaningful difference of 3 kg (133, 176-180) in 6 mos. weight loss between the *IH* and *GR* arms, with 80% power and a type 1 error rate of 0.05, assuming a common standard deviation of 6 kg, will require 64 participants/group. Secondarily, we will have 70% power to detect a 3 kg difference in a completer analysis with an attrition rate of 20%; however, we expect attrition will be lower based on experience (71, 78, 181), and our use of retention/incentive strategies to minimize loss to follow-up. Thus, a sample of 64/group will provide adequate power for both our primary intent-to-treat analysis with imputed missing data (power = 80%) and our secondary completer only analysis (70%).

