Exploratory aims will examine the influence of the following on weight loss at 6 mos.: behavioral session attendance, compliance with the recommendations for diet (energy intake, number of meals/shakes, servings of fruits/vegetables), PA (min of moderate-vigorous PA, min sedentary time), self-monitoring of diet and PA, sleep, and medications assessed over the time period of interest, i.e. (0-6 and 0-18 mos.) and the change in self-efficacy for PA and dietary change, dietary self-regulation, social support for diet/PA, and barriers to PA from 0-6 mos. We will examine the influence of these factors as covariates, in addition to treatment, on weight loss at 6 mos. As we have 128 observations with a rule of thumb of at least 30 observations for each variable in the model, judicious model selection will be completed as we can only expect to identify ~ 4 variables that are related to weight loss in a single model. First, we will assess if these variables differ by treatment at the 0.10 level and if they do they will be considered for future modeling. If in a two-factor model, the variable and treatment have a potential interaction at the 0.10 level that interaction will be considered for future modeling. Subsequently, the main effects and interaction effects along with treatment will be examined in a joint model. Given the pitfalls of forward and backward selection, we will utilize best subsets criteria based upon Mallow's Cp statistic to produce the most parsimonious and least biased model of weight loss at 6 months. This should allow us to identify what variables most highly influence our outcome along with treatment and/or the mechanism(s) of action that are impacting weight loss. We will do the same for weight loss at 18 months, as this measure may have similar or different variables that impact this long-term outcome.

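### Do the counselling frequency in the power rationale and the 5% label on 8.5 kg undermine the sample size of 64 per group?

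*Combined protocol and SAP*

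**What the plan says.** The Power/sample size paragraph builds its rationale in three steps. In the prior trial, the mean 6-month loss with "eSLD and behavioral counseling delivered by monthly home visits, was 5.5 kg". Next, "This does not reach the 8.5 kg (~5%) average 6 mo. weight loss defined as clinically meaningful", a benchmark that the plan attributes to a weight management guideline. Finally, the loss in the GR arm, "which includes weekly group counseling and group exercise, will reach or exceed 8.5 kg". The paragraph then sizes the trial on a 3 kg difference, with separate citations for its clinical relevance, and a common SD of 6 kg. It states 64 per group, 80% power, and 70% power in completers at 20% attrition.

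The section on behavioral session frequency and duration gives GR two sessions a month through month 12. It adds: "Behavioral sessions in the IH arm will follow the same frequency as the GR arm and will occur 2/mo". Aims and Hypotheses says "Both groups will receive identical attention with 2 interventions having the potential for clinically meaningful weight loss", and Study Type and Design lists as a strength "Controlling for attention by maintaining equal contact in both groups".

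The Weight management part of the Background describes the prior trial as including "self-monitoring (logs), and optional PA", and reports a mean 6-month loss of 4.1% on the enhanced Stop Light Diet (eSLD). The exploratory aims list "behavioral session attendance, compliance with the recommendations for diet" among the factors to be related to weight loss.

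**The concern.** Three features of the power rationale sit badly with the rest of the plan.

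- **Counselling frequency.** The rationale credits GR with weekly counselling, while the schedule says twice a month in both arms. Weekly counselling in GR alone would also contradict the claims of identical attention and equal contact. If attendance were analysed as a share of scheduled sessions, the two descriptions would give different denominators.
- **The 5% label.** If 8.5 kg is 5% of body weight, the mean participant weighs 170 kg, close to the entry cap of 400 lb. A mean loss could then meet the plan's 5% standard for clinically meaningful loss and still miss 8.5 kg.
- **The comparator figure.** The 5.5 kg comes from monthly visits with optional physical activity. The scheduled IH arm has two sessions a month, an activity target, and weekly calls and messages, so its loss might be larger.

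Because 8.5 − 5.5 = 3, these sentences are what make the 3 kg difference look attainable. If that difference depended on them, the sample size would be in doubt.

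**Working it through.** **1. The plan's own figures.** Inputs from Power/sample size and Analysis plans: difference 3 kg, SD 6 kg, alpha 0.05 (sidedness not stated; two-sided assumed), two-sample t-test, equal allocation.

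- Normal approximation: n = 2 × (1.960 + 0.842)² × 6² / 3² = 2 × 7.849 × 4 = 62.8, so 63 per group. The noncentral t calculation gives 63.77, so 64.
- At 64 per group, the noncentrality is 3 / (6 × √(2/64)) = 2.83, and power is 80.1%.
- With 20% attrition, 64 × 0.8 = 51.2, taken as 51. The noncentrality is 3 / (6 × √(2/51)) = 2.52, and power is 70.6%.
- A one-sided test would need only 50 per group, so the plan evidently used two sides.

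All three stated figures reproduce. Counselling frequency, 8.5 kg, 5% and 5.5 kg appear nowhere in the formula.

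**2. Counselling sessions in months 0-6.** Twice a month gives 2 × 6 = 12; weekly gives 26; the difference is 14.

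Ten sessions attended would be 10/12 = 83% or 10/26 = 38%. The plan does not say that attendance will be a percentage. If it is, and both arms share one schedule as the Behavioral session section says, every count is divided by the same constant. The regression coefficient rescales, but its test, any interaction test and Mallows' Cp do not change. A distortion would need a different denominator in each arm, which that section rules out.

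**3. Weight implied by the 5% label.**

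- 8.5 / 0.05 = 170 kg (375 lb), against a cap of 400 lb = 181.4 kg. Reading about 5% as 5.5% still gives 8.5 / 0.055 = 155 kg.
- Prior trial: 5.5 / 0.041 = 134 kg. Rounding alone gives 5.45 / 0.0415 = 131 kg to 5.55 / 0.0405 = 137 kg. This assumes that both figures come from the same arm and analysis set, and it uses a ratio of means in place of a mean of ratios.
- Cross-check from the prior trial's BMI of about 44, with assumed mean heights of 1.60 to 1.80 m: 44 × 1.60² = 113 kg to 44 × 1.80² = 143 kg.
- At 134 kg, 5% is 6.7 kg and 8.5 kg is 6.3%.

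The label fits poorly. However, the plan states no expected baseline weight and takes 8.5 kg from a guideline, so the label may describe a different population.

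**4. Where 8.5 kg is used.** The primary analysis compares arm means. The responder endpoint is an individual loss of at least 5% at 18 months. No planned test or decision refers to 8.5 kg.

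**The case for a change.** The strongest case for a change is that 3 kg is exactly 8.5 minus 5.5, so the narrative carries the credibility of the effect size even though it is absent from the formula. Suppose GR were expected to lose only 5% of 134 kg, or 6.7 kg. The gap from 5.5 kg would be 1.2 kg, and power at 64 per group would be about 20%. A more intensive IH arm could narrow the gap further.

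This stands as a comment on how optimistic the expectation is. It does not show an error in the sample size. The plan calls 3 kg a clinically meaningful difference and cites sources for that, and powering a trial for the smallest difference worth detecting is legitimate whatever the expected effect. The 20% figure depends on the inferred 134 kg and on GR stopping at exactly 5%, neither of which the plan states. Rewording the paragraph would leave the true effect and the power unchanged.

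The gap between the prior protocol and the present IH arm is largely disclosed. The power paragraph itself mentions monthly visits, the Background mentions optional activity, and Aims and Hypotheses calls IH an enhanced and modified version of the earlier programme.

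The frequency contradiction also stands as text. Settling it would not by itself establish equal contact, because GR also has two 30-minute group exercise sessions a week in months 0-6, against one call of 5-10 minutes and one message a week in IH.

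**Conclusion.** No change to the plan follows. The mention of weekly counselling is a clerical inconsistency in a rationale. It conflicts with the section that sets out the schedule for both arms, and the two passages should be reconciled when the text is next edited. The 5% label is a loose gloss whose basis could be stated. The mismatch of 170 kg against about 134 kg is inferred under the assumptions above and is not a conflict between two stated weights. How to express attendance is a gap that an analyst can fill sensibly from the schedule.

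In size, the frequency statements differ by 14 sessions over six months, and the effect on the sample size, power, tests and endpoints is nil: 64 per group, 80.1% and 70.6% all stand. That confirms the arithmetic from the stated inputs only. It does not endorse the 3 kg and 6 kg themselves, the treatment of imputed outcomes as fully informative, or the absence of an allowance for GR counselling groups of 10-15, which are separate questions.
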